5.4 Safety Variables

Assessment of the primary safety objective and other safety objectives will be performed on all subjects exposed to RBX2660 (Safety Population, see Section 6.3.1), and will include descriptive statistics. Additional sub-analyses of safety data may be performed on sub-populations.

5.4.1 *Primary Safety Endpoint*

Number of subjects with investigational product- and/or enema-related treatment-emergent adverse events (TEAEs).

5.4.2 *Other Safety Endpoints*

1. Number of adverse events per subject
2. Timing of attributable TEAEs
3. Duration of TEAEs
4. Relatedness of TEAEs
5. Severity of TEAEs
6. Causality of TEAEs to IP, enema, *C. difficile* or prior condition
7. Number of each of the following CDI-related TEAEs through 8-weeks post treatment: death, septic shock, toxic megacolon, colonic perforation, emergency colectomy, and intensive care unit (ICU) admission
8. Onset of new chronic conditions relative to treatment administration

5.4.3 *Adverse Events*

An adverse event (AE) is any untoward medical occurrence associated with the use of IP, whether or not the event is considered product-related. Preexisting conditions that worsen in frequency, intensity or character of the condition during study participation will be recorded as an AE. AEs will be recorded for each subject from the day of enrollment through the 6-month telephone assessment. Serious adverse events (SAEs) will be recorded for each subject from the day of enrollment through the duration of the study.

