6.6 Safety Analysis

The SP will be used to summarize all adverse event data, unless otherwise specified. Safety data will be summarized for events after the first and second enemas, as well as combined. Events occurring after the first enema will be counted up to the date of retreatment, or study exit. Events on, or after, the date of a second enema will be assigned to the second period. The combined analysis will consider all events, after first enema through study exit, even if a subject receives a second enema.

6.6.1 *Analyses Supporting the Primary Safety Endpoint*

Assessment of the primary safety objective will include descriptive statistics and be performed on the SP. Additional sub-analyses of safety data may be performed on sub-populations.

6.6.2 *Other Safety Analyses*

6.6.2.1 *Adverse Events*

A summary of adverse events, TEAEs, non-serious TEAEs, and serious TEAEs will be summarized using counts of the number of events and frequencies (counts and percentages) of

the number of subjects. The incidence of each preferred term (PT) within the primary system organ class (SOC) as well as overall primary SOC incidence will be presented. Summaries may also be presented by PT, irrespective of SOC. A subject with multiple events coded to the same PT within a primary SOC will be counted only once for the PT within the primary SOC. Likewise, a subject with multiple events coded to the same SOC will be counted only once within the SOC.

An overall summary of AEs will present the incidence of (1) all TEAEs, (2) TEAEs related to IP, (3) TEAEs related to enema procedure, (4) TEAEs related to *C. difficile* disease, (5) TEAEs related to a preexisting condition, (6) serious TEAEs, (7) serious TEAEs related to IP, (8) serious TEAEs related to the enema procedure, (9) serious TEAEs related to *C. difficile* disease, (10) serious TEAEs related to a preexisting condition, and (11) TEAEs leading to death.

Frequency of occurrence and number and percent of subjects experiencing an event through 6 months follow-up will be presented for both the first and second enemas as follows:

- All TEAEs
- TEAEs by maximum severity
- TEAEs by relatedness to IP
- TEAEs by relatedness to *C. difficile* disease
- TEAEs by relatedness to enema procedure
- TEAEs by relatedness to preexisting condition
- TEAEs resulting in subject withdrawal
- TEAEs resulting in death
- Serious TEAEs
- Serious TEAEs by maximum severity
- Serious TEAEs by relatedness to IP

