- Serious TEAEs by relatedness to *C. difficile* disease
- Serious TEAEs by relatedness to enema procedure
- Serious TEAEs by relatedness to preexisting condition
- Serious TEAEs resulting in subject withdrawal
- Serious TEAEs resulting in death

For the summary of AEs by maximum severity, if a subject has multiple events occurring in the same SOC or same PT, then the event with the highest severity will be counted. For AEs reported by causality, if a subject has multiple events occurring in the same SOC or same PT, the event with the highest association will be summarized.

A summary of TEAE and serious TEAE characteristics (severity, relatedness to IP, relatedness to *C. difficile* disease, relatedness to enema procedure, and relatedness to preexisting condition by outcome) will also be presented by first and second enema and overall.

Incidence of AEs and serious AEs will also be presented by onset interval separately for the first and second enemas (as applicable), as well as a combined presentation for the following intervals:

- Baseline (onset date prior to date of first enema)
- IP administration (onset date on the date of the first and second enema, as applicable)
- Intervals relative to the enema date (first and second enemas, as applicable):
 - 1-Week (day 8), 4-Weeks (day 29), 8-Weeks (day 57), 4 Months (Day 120), and 6 Months (Day 180).

For data presentation, SOC will be ordered alphabetically, with PT sorted by decreasing total frequency. No inferential statistics will be provided for the AE data.

Subject listings will be presented for all AEs including SAEs.

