6.6.2.5 Subject Diary including Solicited Adverse Events and Completion Compliance

All solicited adverse events recorded in the Subject Diary will be summarized utilizing frequencies (number of events), proportions (number of subjects with the event) and 95% CIs for categorical variables and using the descriptive statistics as listed in **Section 8.1** for continuous variables.

For each solicited event, severity scores will be summarized as both categorical and continuous values. For continuous summaries, severity scores will be identified as either pre-treatment or post-treatment (all diary entries captured after the first enema), and the average for each period will be calculated across individual subjects. Baseline for continuous summaries will be considered the average during the pre-treatment period. For categorical summaries, if a subject reports more than one severity score on the same date, the maximum severity will be used. Baseline for categorical summaries will be considered the last non-missing assessment prior to the enema.

For each categorical summary of event frequency, a two-sided 95% CI will be calculated using the normal approximation of the binomial.

The following summaries will be produced for the first enema:

- Frequency of severity scores on day of enema administration
- Frequency of severity scores on day 1 through 1-week post-treatment
- Frequency of maximum post-treatment severity score

Compliance in returning completed Subject Diaries will be calculated by dividing the number of diaries turned in, whether complete or not, by the number of diaries expected to be turned in. Furthermore, compliance will be summarized by calculating the proportion of subjects who turned in “complete” diaries, where complete is defined as answering all 14 daily questions (e.g.

11 solicited AE, Bristol Stool Type, New illnesses/injuries, New medications) for at least 80% of the expected number of diaries.

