7 STATISTICAL METHODS

7.1 General Methodology

Data will be summarized using descriptive statistics with SAS® Version 9.3 or higher. Confidence intervals (CI) will be constructed at the level of 95% unless specified otherwise. For continuous variables, descriptive statistics (number of subjects [N], mean, standard deviation [SD], median, inter-quartile range [IQR], minimum, and maximum) will be generated. For discrete/categorical variables, the number and percentage of non-missing subjects will be generated. Standard operating procedures (SOPs) will be followed in the creation, validation and quality control of all data displays and analyses.

Subject listings of all data from the eCRFs as well as any derived variables will be presented.

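### The SAP plans no confidence interval for the primary safety endpoint, gives one to solicited diary events, and computes that one by a method that fails at low counts

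*SAP*

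**What the plan says.** - **Primary endpoint (SAP 5.4.1; Protocol 6.4).** It is worded as a number of subjects, namely those with a treatment-emergent adverse event related to the investigational product and/or the enema.
- **Its analysis (SAP 6.6.1).** "Assessment of the primary safety objective will include descriptive statistics and be performed on the SP". No interval is named. Protocol 12.2 likewise promises only descriptive statistics.
- **Related-event tables (SAP 6.6.2.1).** These show event counts, and counts and percentages of subjects. The section then says "No inferential statistics will be provided for the AE data".
- **Solicited events from the diary (SAP 6.6.2.5).** "For each categorical summary of event frequency, a two-sided 95% CI will be calculated using the normal approximation of the binomial".
- **General rules (SAP 7.1).** "Confidence intervals (CI) will be constructed at the level of 95% unless specified otherwise". For categorical data: "For discrete/categorical variables, the number and percentage of non-missing subjects will be generated".
- **Sample size (SAP 3.3).** Up to 750 subjects are treated, with no power calculation.

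**The concern.** This is a single-arm safety study with no comparator, no hypothesis test and no power calculation. Its main quantitative contribution is an estimate of how often related events occur in a broader population, together with how precise that estimate is. The plan supplies the estimate but not the precision for the primary endpoint, while it does supply intervals for solicited diary events. A programmer who follows 6.6.1, 6.6.2.1 and 7.1 as written would produce a number and a percentage and stop.

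A second weakness follows. The only interval method named in the safety section is the normal approximation. The diary summaries are broken down by severity grade, so some cells may be at or near zero, where that method gives impossible or empty intervals.

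**Working it through.** **1. Does any section commit to an interval for the primary endpoint?**

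| SAP section | Covers | Interval? |
|---|---|---|
| 6.6.1 | Primary objective | None named; descriptive statistics only |
| 6.6.2.1 | All adverse event tables, including those by relatedness | None; counts and percentages, no inferential statistics |
| 6.6.2.5 | Solicited adverse events from the diary | 95%, normal approximation |
| 7.1 | General rule | Sets the level; does not say which estimates get one. Categorical format is number and percentage |

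There are two ways to read 6.6.2.1. If a confidence interval counts as inferential, the sentence excludes it for adverse event data, and 6.6.2.5 conflicts with it because solicited events are adverse events too. If an interval does not count as inferential, nothing excludes one, but nothing plans one for the primary endpoint either. On both readings the primary endpoint has no planned interval.

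**2. Is the combined count itself tabulated?** The overall summary in 6.6.2.1 lists product-related and enema-related events as separate items. A subject may appear in both, so the two cannot be added, and no listed table gives the and/or count.

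**3. The plan's own figure.** The cap of 750 has no power, error rate or target precision behind it, so there is no calculation to reproduce.

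**4. How the named method behaves at n = 750.** The formulas for x events among n subjects, with p = x/n, are:

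- Normal approximation: p ± 1.96 × √(p(1 − p)/n).
- Exact (Clopper-Pearson): lower limit is the 2.5% point of Beta(x, n − x + 1); upper limit is the 97.5% point of Beta(x + 1, n − x). For x = 0 the upper limit is 1 − 0.025^(1/n).

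For x = 0, the normal approximation has p = 0 and zero width, so it gives 0 to 0%. The exact upper limit is 1 − 0.025^(1/750) = 0.49%.

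For x = 3, p = 0.40%. The half-width is 1.96 × √(0.004 × 0.996/750) = 0.45 points, giving -0.05 to 0.85%. The exact interval is 0.08 to 1.16%.

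**5. What the missing interval would look like.** The rate is an assumption, taken from the retrospective study 2019-02 (Protocol 5.3.5): 11 subjects (17.2%) with product-related events and 3 (4.7%) with enema-related events. The implied denominator is 64, since 11/64 = 17.2% and 3/64 = 4.7%. The overlap is not given, so the combined rate lies between 11/64 = 17.2% (full overlap) and 14/64 = 21.9% (none). At 750 treated these correspond to 129 and 164 subjects.

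| Treated | Subjects with event | Rate | Exact 95% interval | Normal approximation |
|---|---|---|---|---|
| 750 | 129 | 17.2% | 14.6 to 20.1% | 14.5 to 19.9% |
| 750 | 164 | 21.9% | 19.0 to 25.0% | 18.9 to 24.8% |
| 400 | 69 | 17.25% | 13.7 to 21.3% | 13.6 to 21.0% |
| 200 | 34 | 17.0% | 12.1 to 22.9% | 11.8 to 22.2% |

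At these rates the two methods nearly agree, so the choice of method matters for rare events rather than for the primary endpoint. With 0 events the exact upper limit rises from 0.49% at 750 to 0.92% at 400 and 1.83% at 200.

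**The case against.** The strongest reply is that the SAP does not forbid an interval. The sentence on inferential statistics closes 6.6.2.1, under the heading for other safety analyses, while the primary endpoint has its own section, 6.6.1, with no such restriction. The SAP never says that an interval is inferential, and by attaching intervals to solicited adverse events it suggests that it means hypothesis tests. This stands. A reader might infer that the primary endpoint is expressly barred from having an interval, and the documents do not support that. They support the narrower statement that none is planned and that the sections are not consistent.

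A reader might also take 7.1 to grant 95% intervals by default, with 6.6.2.1 as the exception. Its wording more naturally concerns the level, so it neither grants an interval to the primary endpoint nor is overridden.

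It can further be said that the consequence is modest, because anyone can compute a binomial interval from the reported counts and no decision rule depends on it. That also stands, provided the combined and/or count is reported. It would be too strong to say that the study could not state what rate it rules out.

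Finally, the documents do not show that individual diary items will be rare. In study 2013-001, 51.5% of subjects after one treatment and 41.7% after two reported some solicited event on Day 7 (Protocol 5.3.1). Those figures are for any event, though, not for each item by severity grade.

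**Conclusion.** The point holds as a gap in specification and an inconsistency. No section plans an interval for the primary endpoint, 6.6.2.5 plans one for solicited events, and the method named there breaks down at or near zero counts: 0 to 0% against an exact upper limit of 0.49% for 0/750, and -0.05 to 0.85% against 0.08 to 1.16% for 3/750.

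For the primary endpoint, the omitted precision statement would be about ±2.7 to ±3.0 points at the cap. This assumes a true rate in the range 17.2 to 21.9% carried over from study 2019-02, and 750 treated. Since 750 is a ceiling, the interval would be wider with fewer subjects. The 0/750 and 3/750 figures illustrate rare outcomes such as related serious events or sparse diary cells; they are not forecasts for the primary endpoint.

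No error rate, power or sample size is affected.

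**What to change.** 1. In SAP 6.6.2.1, replace the sentence on inferential statistics with: *No hypothesis tests will be performed for AE data.*
2. In SAP 6.6.1, state that the primary endpoint is the combined count of subjects with at least one product- and/or enema-related treatment-emergent event, each subject counted once. Report it as n (%) of the Safety Population with an exact (Clopper-Pearson) 95% confidence interval. Do the same for related serious events.
3. In SAP 6.6.2.5, replace the normal approximation with the exact method.

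The cost is a few SAP sentences, one combined row and an interval column in the tables. No new data are needed and study conduct does not change. This is a free improvement.

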6.6.2.2 Major Complications of CDI events

Major complications of CDI events include death, septic shock, toxic megacolon, colonic perforation, emergency colectomy, or ICU admission collected through the 6-month telephone assessment after the last study enema. Incidence of major complications of CDI events will be summarized by the first and second enemas.

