When assessed by maximum severity per subject, the majority of TEAEs (317/368, 86.1%), reported in 147 subjects (82.6%), were assessed as mild-to-moderate, 12.5% (46/368) TEAEs were severe, and 1.4 % (5/368) TEAEs were potentially life-threatening. The most frequently occurring TEAEs (256/708, 36.2%) were related to gastrointestinal disorders as would be expected in this population. Of the 54 serious TEAEs reported throughout the study, as assessed by investigator, none (0) were related to IP, none (0) were related to enema procedure, 16 (29.6%) events were related to *C. difficile* disease, and 40 (74.1%) events were related to a pre-existing condition. Of serious TEAEs that occurred within 8 weeks of the blinded period, 20 events occurred in 13 (4.9%) of subjects. Death was reported in 2 subjects, none (0) were reported as related to IP or enema procedure; both deaths were the result of AEs related to a pre-existing condition (one fatal event of multimorbidity; one fatal event of cardio-respiratory arrest).

Overall Conclusions:

Overall, the primary efficacy endpoint of study 2017-01 met the pre-specified success criteria and demonstrated clinically meaningful results. The efficacy outcomes demonstrated that RBX2660 was superior to Placebo at reducing recurrence of CDI through 8 weeks after completing blinded treatment, response was durable through 6 months, and the safety profile is acceptable for this patient population. In summary, RBX2660 has demonstrated a positive benefit-risk profile for the reduction of CDI recurrence in adult patients following antibiotic therapy for rCDI.

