6.6. Safety Endpoints

1. Number of adverse events per subject

2. Timing of attributable TEAEs
3. Duration of TEAEs
4. Relatedness of TEAEs
5. Severity of TEAEs
6. Causality of TEAEs to IP, enema, *C. difficile* or prior condition
7. Number of each of the following CDI-related TEAEs through 8-weeks post treatment: death, septic shock, toxic megacolon, colonic perforation, emergency colectomy, and ICU admission
8. Onset of new chronic conditions relative to treatment administration

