5.4.3.4 Treatment-Emergent Adverse Events

Adverse events will be considered treatment-emergent adverse events (TEAE) according to the following algorithm:

- If the complete onset date of an AE is known, then:
 - If AE onset date is prior to initial treatment date, then the AE will not be considered treatment-emergent.

- If AE onset date occurs after IP exposure on or after initial treatment date, then the AE will be considered treatment-emergent.
 - If AE onset date is partially known, then:
 - If day is unknown, and month/year occurs on or after first enema month/year, then AE will be considered treatment-emergent. Otherwise, AE will not be considered treatment-emergent.
 - If month/day is unknown, and year occurs on or after first enema year, then AE will be considered treatment-emergent. Otherwise, AE will not be considered treatment-emergent.

5.4.4 *Other Observations Related to Safety*

5.4.4.1 *Solicited Adverse Events*

The following list of anticipated adverse events are solicited from subjects via the Subject Diary from the date of enrollment through the 7th day after receiving the study treatment.:

- gas (flatulence)
- abdominal distension or bloating
- rectal irritation or pain
- chills/severe shivering
- abdominal pain or cramping
- increased diarrhea
- constipation
- rectal bleeding
- nausea
- vomiting
- fever $\geq 37.8^{\circ}\text{C}$ ($\geq 100.0^{\circ}\text{F}$)

Frequency and severity of the solicited AEs will also be captured in the Subject Diary.

5.4.4.2 *Major Complications of CDI Events*

Frequencies of major complications of CDI including death, septic shock, toxic megacolon, colonic perforation, emergency colectomy, or ICU admission will be collected through the 6-month telephone assessment after the last study enema.

5.4.4.3 *Hospitalizations for Recurrent CDI*

Details regarding hospitalizations due to CDI, including admission and discharge date/time, reason for admission, whether the subject was admitted to an ICU, and ICU admission and discharge date/time (if applicable), will be collected following both the first and second study enemas

5.5 **Efficacy Variables**

5.5.1 ***Efficacy Endpoint***

Assessment of secondary objectives will include descriptive statistics and be performed on pre-defined analysis populations including Intent-to-Treat (ITT), modified Intent-to-Treat (mITT) and Per-Protocol (PP). Additional sub-analyses of safety data may be performed on sub-populations.

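### The 8-week safety endpoint of CDI-related major complications has no planned output: SAP 6.6.2.2 summarises those events through the 6-month call, without an 8-week cut

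*SAP*

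**What the plan says.** **Endpoint.** Protocol 6.6 item 7 reads "Number of each of the following CDI-related TEAEs through 8-weeks post treatment: death, septic shock", and goes on to toxic megacolon, colonic perforation, emergency colectomy and ICU admission. The protocol synopsis has the same item. SAP 5.4.2 item 7 repeats it: "Number of each of the following CDI-related TEAEs through 8-weeks post treatment".

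**Collection.** SAP 5.4.4.2 states that frequencies of these complications "will be collected through the 6-month telephone assessment after the last study enema".

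**Analysis.** SAP 6.6.2.2 lists the same six events and describes them as "collected through the 6-month telephone assessment after the last study enema". Its one analysis sentence is: "Incidence of major complications of CDI events will be summarized by the first and second enemas".

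**General counting rule.** SAP 6.6 says: "Events occurring after the first enema will be counted up to the date of retreatment, or study exit". Events from the date of a second enema onward go to the second period.

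**Neighbouring section.** SAP 6.6.2.3 summarises hospitalizations for recurrent CDI through 8 weeks and adds a listing for the whole study.

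SAP 4.1 declares no change to the planned analysis, so 6.6.2.2 is not presented as a departure from the protocol.

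**The concern.** The endpoint lists and the analysis section give different windows for the same six events. A programmer who follows 6.6.2.2 and the general rule in 6.6 would count every complication up to retreatment, study exit or the 6-month call. The resulting table would appear to report endpoint 7 but would answer another question.

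Two things are at stake. The number reported for a pre-specified safety endpoint would not be the number the protocol promised, and it could not be set beside the study's other 8-week results, such as CDI recurrence. In addition, the first-enema column would pool subjects with very different lengths of follow-up, which a fixed 8-week window largely avoids.

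**Working it through.** The plan states no figure for this endpoint, so there is none to reproduce. The check has three parts.

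**1. Length of the windows**

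Inputs:
- Endpoint window: days 1-57 (SAP Table 3, 0-8-week row).
- 6-month point: day 180 (SAP 6.6.2.1; Table 3 ends at 180+).
- End of the 6-month call window: day 194 (SAP Table 2).

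Results for a subject who is not retreated:
- Ratio of windows: 180/57 = 3.2; at the end of the call window, 194/57 = 3.4.
- Share of the 6.6.2.2 window that belongs to the endpoint: 57/180 = 31.7%; 57/194 = 29.4%.
- Share outside the endpoint: 68.3% and 70.6%.

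**2. Unequal first-enema follow-up**

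Under SAP 6.6 the first-enema period ends at retreatment or study exit. Retreatment requires failure within 8 weeks and must follow within 21 days of failure determination. If failure is determined by day 56, the longest first-enema period for a retreated subject is 56 + 21 = 77 days, and it can be much shorter. A subject who is not retreated contributes about 180 days.

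**3. Whether another output supplies the endpoint**

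| SAP output | Window | Limited to CDI-related events? | Components covered |
|---|---|---|---|
| 6.6.2.2 major complications | 6 months | Implied by the title | All six |
| 6.6.2.1 AEs and serious AEs by onset interval | Includes days 1-57 | No | Only those that appear as AE terms |
| 6.6.2.1 TEAEs by relatedness to *C. difficile* | 6 months | Yes | Only those that appear as AE terms |
| 6.6.2.1 TEAEs resulting in death | 6 months | No | Death |
| 6.6.2.3 hospitalizations for recurrent CDI | 8 weeks | Yes | ICU admission during those hospitalizations |

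No row combines the 8-week window, the CDI restriction and all six components. Preferred-term tables could not do so alone. Protocol 11.1 records the condition behind a procedure rather than the procedure, so emergency colectomy should not appear as an AE term. Death and ICU admission are outcomes or levels of care rather than AE terms.

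**Illustration of the effect on counts.** The documents give no complication rate. Assume that the daily rate on days 1-57 is k times the rate on the remaining 180 − 57 = 123 days, for a subject followed throughout. The share of tabulated events that belongs to the endpoint is then 57k / (57k + 123):

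| k | 1 | 2 | 3 | 5 | 10 |
|---|---|---|---|---|---|
| Share | 32% | 48% | 58% | 70% | 82% |

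The values of k are assumptions. The range shows only that the effect could be large or modest.

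**The case against.** The best defence is that the 6-month phrase in 6.6.2.2 describes data capture. Capture to 6 months contains the 8-week data, the definition in 5.4.2 stays in force, and Table 3 already supplies a days 1-57 window. On that view the section only lacks a cross-reference. It is true that long capture is no error. But the capture period was already stated in 5.4.4.2. Section 6.6.2.2 repeats it in the analysis text and adds no narrower rule, the general rule in 6.6 does not supply one, and 6.6.2.3 states its 8-week cut explicitly. The plain reading of 6.6.2.2 is therefore a count through 6 months.

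It is also fair to say that ICU admission is partly covered at 8 weeks by 6.6.2.3, and that the endpoint is descriptive, non-primary and recoverable from onset dates. Both points stand, and they limit the importance of the gap.

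A reader might infer more than the documents support:

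- **That the table mixes first- and second-enema events.** It does not. Sections 6.6 and 6.6.2.2 separate them. Only the unequal length of the first period is a valid complaint.
- **That counts would rise about 2.7-fold.** Protocol 5.3.4 reports, for study 2017-01, "Of serious TEAEs that occurred within 8 weeks of the blinded period, 20 events occurred in 13 (4.9%) of subjects", against 54 serious TEAEs in the whole study, and 54/20 = 2.7. But the 20 cover only 8 weeks of the blinded period and omit the 8 weeks after any later treatment. Both figures also count all serious TEAEs, not these complications. For all TEAEs in that study the comparable ratios are 708/401 = 1.8 (blinded treatment) and 708/478 = 1.5 (either treatment). None of these is a complication ratio.
- **That the CDI restriction is lost, adding a further factor of about 3.** In 2017-01, 16 of 54 serious TEAEs were related to *C. difficile* (54/16 = 3.4). But 6.6.2.2 concerns complications of CDI, which implies the link. What is missing is the rule for deciding it.

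**Conclusion.** The mismatch is real and should be corrected. As written, SAP 6.6.2.2 uses a window of about 180 days for a 57-day endpoint, 3.2 times as long (3.4 at the end of the call window), and no planned output reports endpoint 7 as defined. This rests on the plain reading of 6.6.2.2 together with 6.6, and on Table 3 for the day counts. The 3.2 is a ratio of window lengths and should not be read as inflation of event counts, which the documents do not allow anyone to estimate. The consequence is moderate: no inference or sample size depends on this endpoint, and the data for the correct count will exist.

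**What to change.** In SAP 6.6.2.2:

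1. Tabulate each of the six components that is CDI-related, with onset on days 1-57 (Table 3, 0-8-week window) after the first enema, and separately with onset on days 1-57 after the second enema, counting the second enema date as day 1.
2. State that the first-enema count stops at retreatment, as 6.6 already provides, and show how many subjects were retreated before day 57.
3. State how CDI-related is decided, for example by the investigator's rating of relatedness to *C. difficile* disease in SAP 5.4.3.3.
4. Identify death, emergency colectomy and ICU admission from the complication and hospitalization data collected under SAP 5.4.4.2 and 5.4.4.3, rather than from AE preferred terms alone.
5. Keep the 6-month count as a supplementary column, labelled as such.

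The cost is a few sentences of SAP text and one table. The data are already planned for collection, and the protocol's endpoint definition does not change.
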